### **6.1.1 Source Documents**

Source documents are defined as original documents, data and records. This may include hospital records, clinical and office charts, laboratory data/information, patients' diaries or evaluation checklists, pharmacy dispensing and other records, recorded data from automated instruments, microfiches, photographic negatives, microfilm or magnetic media, X-rays. The investigator will permit trial-related monitoring, audits, IRB review, and regulatory inspection(s), providing direct access to source documents.

### **6.1.2 Case Report Forms**

Data may be entered from the source documents directly into eCRFs in C3D for each patient enrolled in this study. The principal investigator or research nurse will review the eCRFs for completeness and accuracy. Independent audits may also be conducted by NCI personnel to ensure completeness and accuracy of data in C3D.

## **6.2 DATA SHARING PLANS**

### **6.2.1 Human Data Sharing Plan**

I will share human data generated in this research for future research as follows:

1. Coded, linked data in an NIH-funded or approved public repository.
2. Coded, linked data in BTRIS (automatic for activities in the Clinical Center)
3. Identified or coded, linked data with approved outside collaborators under appropriate agreements.

Data will be shared through:

1. An NIH-funded or approved public repository. Insert name or names: `_clinicaltrials.gov`, `dbGaP`.
2. BTRIS (automatic for activities in the Clinical Center)
3. Approved outside collaborators under appropriate individual agreements.
4. Publication and/or public presentations.

Data will be shared:

- a) Before publication.
- b) At the time of publication or shortly thereafter.

### **6.2.2 Genomic Data Sharing Plan**

Unlinked genomic data will be deposited in public genomic databases such as dbGaP in compliance with the NIH Genomic Data Sharing Policy.

### **6.3 RESPONSE CRITERIA**

For the purposes of this study, patients should be re-evaluated for response every 8 weeks +/- 4 days with imaging modalities determined appropriate by the investigators. In addition to a baseline scan, confirmatory scans should also be obtained 4 weeks +/- 4 days following initial documentation of objective response.

Response and progression will be evaluated in this study using the new international criteria proposed by the revised Response Evaluation Criteria in Solid Tumors (RECIST) guideline (version 1.1).(40) Changes in the largest diameter (unidimensional measurement) of the tumor lesions and the shortest diameter in the case of malignant lymph nodes are used in the RECIST criteria.

#### **6.3.1 Disease Parameters**

Measurable disease: Measurable lesions are defined as those that can be accurately measured in at least one dimension (longest diameter to be recorded) as:

1. By chest x-ray:  $\geq 20$  mm;
2. By CT scan:
  1. Scan slice thickness 5 mm or under: as  $\geq 10$  mm
  2. Scan slice thickness  $> 5$  mm: double the slice thickness
3. With calipers on clinical exam:  $\geq 10$  mm.

All tumor measurements must be recorded in millimeters (or decimal fractions of centimeters).

Malignant lymph nodes. To be considered pathologically enlarged and measurable, a lymph node must be  $\geq 15$  mm in short axis when assessed by CT scan (CT scan slice thickness recommended to be no greater than 5 mm). At baseline and in follow-up, only the short axis will be measured and followed.

Non-measurable disease. All other lesions (or sites of disease), including small lesions (longest diameter  $< 10$  mm or pathological lymph nodes with  $\geq 10$  to  $< 15$  mm short axis), are considered non-measurable disease. Bone lesions, leptomeningeal disease, ascites, pleural/pericardial effusions, lymphangitis cutis/pulmonitis, inflammatory breast disease, and abdominal masses (not followed by CT or MRI), are considered as non-measurable.

Note: Cystic lesions that meet the criteria for radiographically defined simple cysts should not be considered as malignant lesions (neither measurable nor non-measurable) since they are, by definition, simple cysts.

'Cystic lesions' thought to represent cystic metastases can be considered as measurable lesions, if they meet the definition of measurability described above. However, if non-cystic lesions are present in the same patient, these are preferred for selection as target lesions.

Target lesions. All measurable lesions up to a maximum of 2 lesions per organ and 5 lesions in total, representative of all involved organs, should be identified as **target lesions** and recorded and measured at baseline. Target lesions should be selected on the basis of their size (lesions with the

longest diameter), be representative of all involved organs, but in addition should be those that lend themselves to reproducible repeated measurements. It may be the case that, on occasion, the largest lesion does not lend itself to reproducible measurement in which circumstance the next largest lesion which can be measured reproducibly should be selected. A sum of the diameters (longest for non-nodal lesions, short axis for nodal lesions) for all target lesions will be calculated and reported as the baseline sum diameters. If lymph nodes are to be included in the sum, then only the short axis is added into the sum. The baseline sum diameters will be used as reference to further characterize any objective tumor regression in the measurable dimension of the disease.

Non-target lesions. All other lesions (or sites of disease) including any measurable lesions over and above the 5 target lesions should be identified as **non-target lesions** and should also be recorded at baseline. Measurements of these lesions are not required, but the presence, absence, or in rare cases unequivocal progression of each should be noted throughout follow-up.

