## 2 ELIGIBILITY ASSESSMENT AND ENROLLMENT

### 2.1 ELIGIBILITY CRITERIA FOR COHORT 1: HORMONE RECEPTOR POSITIVE BREAST CANCER

#### 2.1.1 Inclusion Criteria

- 2.1.1.1 Patients must have histologically confirmed persistent or recurrent invasive metastatic hormone receptor positive, HER2 normal breast cancer for which standard curative measures do not exist or are no longer effective. Hormone receptor positive is defined as estrogen receptor (ER) positive  $\geq 10\%$  by immunohistochemistry (IHC) and/or progesterone receptor (PR) positive  $\geq 10\%$  by IHC. HER2 will be considered negative per ASCO-CAP guidelines (HER2 test result as negative if a single test (or both tests) performed show: 1) IHC 1+ as defined by incomplete membrane staining that is faint/barely perceptible and within  $>10\%$  of the invasive tumor cells; 2) IHC 0 as defined by no staining observed or membrane staining that is incomplete and is faint/barely perceptible and within  $\leq 10\%$  of the invasive tumor cells; or 3) ISH negative based on: a) Single-probe average HER2 copy number  $<4.0$  signals/cell or b) Dual-probe HER2/CEP17 ratio  $<2.0$  with an average HER2 copy number  $<4.0$  signals/cell) and HER2 testing must have been performed in a laboratory accredited by the College of American Pathologists (CAP) or another accrediting entity.
- 2.1.1.2 Patients must have measurable disease, per RECIST 1.1. See Section 6.3.1 for the evaluation of measurable disease.
- 2.1.1.3 Patients must have at least one lesion deemed safe to biopsy and be willing to undergo mandatory biopsies.
- 2.1.1.4 HR+BC patients must have received prior treatment with at least 2 lines of hormonal treatment (SERM, AI, or fulvestrant) and deemed ineligible for further hormonal

*Abbreviated Title: ONC201 in advanced cancers*

*Version Date: 06/17/2020*

therapy . Patients may have received prior chemotherapy and there is no limit to the number of prior chemotherapy.

- 2.1.1.5 Age  $\geq 18$  years.
- 2.1.1.6 ECOG performance status 0 or 1
- 2.1.1.7 Adequate renal function, defined as serum creatinine  $\leq 1.5$  X upper limit of normal (ULN), or measured creatinine clearance  $\geq 60$  mL/min/1.73 m^2.

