## **2.1.2 Exclusion Criteria**

- 2.1.2.1 Patients who have received chemotherapy in the previous 3 weeks (6 weeks for nitrosoureas or mitomycin); other investigational agents within 3 weeks or a PD1/PDL1 agent within 4 weeks prior to first dose of study treatment.
- 2.1.2.2 Patients who have undergone radiotherapy within 4 weeks of first dose of study treatment.
- 2.1.2.3 Patients with a history of another invasive malignancy within the last 3 years.
- 2.1.2.4 Patients with symptomatic brain metastases or leptomeningeal involvement. Patients with asymptomatic or brain metastases that have been treated with radiation at least 4 weeks prior to first dose of study treatment are allowed.

**Abbreviated Title:** *ONC201 in advanced cancers*

**Version Date:** 06/17/2020

- 2.1.2.5 History of allergic reactions attributed to compounds of similar chemical or biologic composition to *imipridones* or other agents used in study.
- 2.1.2.6 Patients with a mean QTcF interval of > 500 msec or receiving therapeutic agents known to prolong the QT interval
- 2.1.2.7 Known history of cardiac arrhythmias including uncontrolled atrial fibrillation, tachyarrhythmias or bradycardia, history of congestive heart failure, or myocardial infarction or stroke in the previous 3 months will be excluded.
- 2.1.2.8 Known history of gastrointestinal illnesses that would preclude the absorption of ONC201, which is an oral agent
- 2.1.2.9 Patients with bone metastases who have initiated denosumab or bisphosphonate therapy within 28 days prior to Cycle 1 Day 1.
- 2.1.2.10 Pregnant women are excluded from this study because ONC201 has the potential for teratogenic or abortifacient effects. Because there is an unknown but potential risk for adverse events in nursing infants secondary to treatment of the mother with ONC201, breastfeeding should be discontinued if the mother is treated with ONC201. These potential risks may also apply to other agents used in this study.
- 2.1.2.11 HIV-positive patients on combination antiretroviral therapy are ineligible because of the potential for pharmacokinetic interactions with ONC201.
- 2.1.2.12 Patients who have known active Hepatitis B, or Hepatitis C infections.

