### 3 STUDY IMPLEMENTATION

#### 3.1 STUDY DESIGN

This is an open label, phase II single arm study of ONC201 divided in three cohorts, each cohort with a different type of metastatic, advanced disease: ER+ BC, TNBC and endometrial cancer. All proposed cohorts require measurable disease based on RECIST criteria and disease that can be biopsied safely. The study will specify a required biopsy prior to treatment and a biopsy during the second cycle after drug treatment. There will also be an optional biopsy at the time of progression. Participants will receive ONC201 starting at the RP2D of 625mg q7 days. Each cycle is 28 days long. ONC201 can be given +/- 1 day due to holidays, inclement weather, conflicts, or similar reasons.

During Cycle 1, patients will receive weekly phone calls by research staff to ask about changes to health and any potential side effects.

While the drug has activity against HER2 amplified breast cancer cells in vitro, we would not initiate a single agent HER2+ cohort at this time because of the clear benefit to HER2 targeted therapies in this subset of breast cancer. We will develop preclinical data for ONC201 in combination with HER2 targeted drugs (*e.g.*, trastuzumab, trastuzumab emtansine, and lapatinib) and plan to initiate a phase I run-in trial at a later date.

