### 5.3 TUMOR BIOPSIES

#### 5.3.1 Timing\*

Biopsies will be performed at the following times:

- Mandatory – after consent, prior to treatment on cycle 1 day 1
- Mandatory - cycle 2 day 2 (< 24 hours of ONC201 dose)
- Optional - at the time of progression

\*Biopsies may be not performed on the specific dates and times due to the following reasons, including but not limited to, delayed recovery of hematologic toxicities, delayed clinic schedule, or national holidays.

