#### 5.3.2 Tissue Sampling and Handling

1. Attempts will be made to obtain up to four cores if safe and feasible. These tumor core biopsies will be obtained percutaneously or per vagina through interventional radiology (for endometrial cancer cohort) as long as considered minimal surgical risk. Two 3-millimeter punch biopsies of skin will be acceptable in lieu of 18-gauge core biopsies for patients with skin involvement. Inability to get tissue with a reasonable attempt will not preclude treatment and the patient will remain eligible for all other translational components.
  - a. Core 1: Electron Microscopy
  - b. Core 2: RNA later buffer
  - c. Cores 3: FFPE
  - d. Cores 4 and 5: OCT
2. The use of imaging to facilitate biopsies will be decided upon by members of the interventional radiology team. Should CT scans be needed for biopsy, a limit of 10 scans for each procedure will be observed to minimize radiation exposure to the patient.
3. The schedule for the biopsies will be made with Special Procedures ([name]). Members of the WMB lab will be on call to receive and embed biopsies: [[contact]](mailto:[contact]), [contact], beeper [name].

*Abbreviated Title: ONC201 in advanced cancers*

*Version Date: 06/17/2020*

4. All cores will be stored, barcoded, in the WMB lab at -80°C on site until use according to our laboratory SOP. See **Table 5** for information about specimen collection and storage.

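### Section 6.3.1 lets a lesion sampled at the mandatory biopsies count in the target sum, so sampling effects on small or single targets could be read as response or progression

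*Combined protocol and SAP*

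**What the plan says.** **Target selection (protocol 6.3.1).** The starting rule is "All measurable lesions up to a maximum of 2 lesions per organ and 5 lesions in total". The selection sentence reads "Target lesions should be selected on the basis of their size" and goes on to require that targets represent all involved organs, "but in addition should be those that lend themselves to reproducible repeated measurements". If the largest lesion cannot be measured reproducibly, the next largest that can is taken.

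**Biopsies.** Section 2.1.1.3, repeated for cohorts 2 and 3, states: "Patients must have at least one lesion deemed safe to biopsy and be willing to undergo mandatory biopsies". Measurable disease is a separate criterion, and nothing says the two must be met by different lesions. Section 3.1 specifies "a required biopsy prior to treatment and a biopsy during the second cycle after drug treatment", and section 5.3.1 places the second on cycle 2 day 2. Section 5.3.2 asks for up to four cores, or: "Two 3-millimeter punch biopsies of skin will be acceptable in lieu of 18-gauge core biopsies for patients with skin involvement".

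**Imaging and confirmation.** Baseline scans may be up to 17 days old (2.9, 3.4). Response is assessed every 8 weeks +/- 4 days, and a response is re-scanned at 4 weeks +/- 4 days (6.3).

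Neither the biopsy sections (5.3.1, 5.3.2) nor the measurement and response sections (6.3.1 to 6.3.3) say which lesion to sample, whether it may be a target, or how to score a lesion altered by sampling.

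**The concern.** A lesion that has been cored or punched may lose tissue, swell or bleed. If its diameter is in the target sum, the change is added to whatever the drug did. With a control arm the effect would fall on both sides; here each cohort is read against a fixed historical rate or median. ORR is primary in cohorts 2 and 3, PFS in cohort 1, and clinical benefit drives early stopping in cohorts 2 and 3. The decision counts are small, so the reading of a single patient can matter. If nobody records which lesion was sampled, its influence may be impossible to examine afterwards.

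**Working it through.** **1. Can the biopsied lesion be a target?** Yes, if it is measurable. When a patient has no more than 2 measurable lesions per organ and 5 in all, the wording makes every one a target, so the biopsied lesion is included. Above those limits, size, organ representation and reproducibility decide; none of them concerns biopsy.

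**2. Does sampling fall between baseline and the first response scan?** With 28-day cycles, cycle 2 day 2 is study day 28 + 2 = 30. Eight weeks after day 1 is day 57. On schedule, the gap is 57 - 30 = 27 days, or 23 to 31 days with the 4-day window. The second biopsy therefore comes after baseline and about 4 weeks before the first scan. The order of the first biopsy and the baseline scan is not fixed, so that biopsy may also come after baseline imaging.

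**3. How large a change matters?** Under 6.3.3.1, PR needs a loss of 0.30 x S from baseline sum S. PD needs a gain of at least max(5 mm, 0.20 x S) from the smallest sum on study.

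| Sum S (mm) | Loss for PR (mm) | Gain for PD (mm) | 3 mm as share of S |
|---|---|---|---|
| 10 | 3.0 | 5 | 30% |
| 20 | 6.0 | 5 | 15% |
| 25 | 7.5 | 5 | 12% |
| 50 | 15.0 | 10 | 6% |
| 100 | 30.0 | 20 | 3% |

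The 10-mm row is the caliper minimum for a measurable skin nodule, and 3 mm is one punch width. The 5-mm floor governs PD up to S = 25 mm, because 0.20 x 25 = 5. These are thresholds, not expected changes: a 3-mm loss assumes that tissue goes along the measured axis and does not heal. The documents give no figure for diameter change after a core biopsy.

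**4. The plan's own figures.** Exact binomial, with cut-offs read from the results that section 10.2 calls interesting (no alpha is stated for cohorts 2 and 3):

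- Cohort 3, at least 4/25: power at 25% is 0.904 (stated 90%); P(X >= 4 | 5%) = 0.034.
- Cohort 2, at least 11/29: power at 45% is 0.829 (stated 82%); P(X >= 11 | 25%) = 0.086.
- Cohort 1: with exponential PFS and an 8-month median, S(4) = 2^(-1/2) = 0.707. A one-sided 0.10 normal-approximation test against 0.50 with n = 24 has power Phi[(0.207 - 1.2816 x sqrt(0.25/24)) / sqrt(0.707 x 0.293/24)] = 0.794 (stated 80%).
- The 80% intervals of 25.7-51.5% (11/29), 4.5-24.8% (3/25) and 7.2-29.5% (4/25) all reproduce.

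**5. What one false response does.** In cohort 3, moving from 3/25 to 4/25 moves the lower 80% limit from 4.5% to 7.2%, across the 5% to be ruled out. It also moves the result from the category described as possibly worth pursuing to the one described as interesting enough to pursue. In cohort 2, the tail probability at 25% is 0.166 for 10 or more responses and 0.086 for 11 or more, so the step from 10 to 11 likewise crosses the one-sided 10% level implied by an 80% interval.

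**The case against.** The strongest reply is that this will rarely matter. Several parts of that stand.

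- Size is not the only criterion. The reproducibility clause gives an investigator a basis for passing over a lesion due to be sampled. That is discretion, not a rule, and it does not ask the question.
- Responses are re-scanned at 4 weeks, which filters transient shrinkage, though not lasting tissue loss. PD has the 5-mm floor, but no confirmatory scan is required for target-lesion progression.
- Section 6.3.2 prefers imaging to calipers where a lesion can be imaged, so caliper-measured, punched targets may be few.
- Roughly 4 weeks between the second biopsy and the scan allows some healing. The documents do not say how much.

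Stronger readings are tempting but not supported:

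- *Every patient has the same lesion sampled twice.* The protocol requires two biopsies, not two of one lesion. The footnote to 5.3.1 allows biopsies to miss their dates, and 5.3.2 says failure to obtain tissue does not preclude treatment. Repeat sampling is forced only if a single lesion can be biopsied.
- *Previously irradiated lesions are an equal gap.* The exclusion is "Patients who have undergone radiotherapy within 4 weeks of first dose of study treatment", with no lesion-level rule for earlier fields. But section 6.3 adopts RECIST 1.1 by reference, and whether it covers such lesions cannot be judged from these documents.
- *Punch area against lesion area shows a PR.* The sum is of diameters, and a given loss of area is a smaller fraction of diameter.
- *The type I error is inflated by a known amount.* Any such figure needs a false-response rate that the documents do not supply, and because sampling can also enlarge a lesion, even the net direction is unknown.

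**Conclusion.** The point holds as a limited one. As written, the protocol allows a biopsied measurable lesion in the target sum, and requires it in patients with few lesions, with at least the second biopsy scheduled between baseline and first assessment. The exposure lies mainly in small or single targets; for sums of about 50 mm or more, changes of 3 to 5 mm reach neither threshold. How many patients are exposed and how often they would be misclassified is unknown. A reader might infer that the design's power or sample size is wrong; it is not, and the stated figures reproduce. The risk is endpoint misclassification in uncontrolled cohorts where one patient can shift the reading, most visibly from 3/25 to 4/25 in cohort 3. This rests on sampling being able to change a measured diameter by a few millimetres in some patients, which is an assumption. The change is worth making because it is cheap.

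**What to change.** Add to section 6.3.1:

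1. Before baseline measurement, name the lesion to be biopsied. When another measurable lesion exists, follow the biopsied one as non-target.
2. If it is the only measurable lesion, keep it as a target and flag the patient. Show ORR and PFS with and without flagged patients as a sensitivity analysis.
3. At each biopsy, record which lesion was sampled.

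No scan, biopsy or reader is added; a few eCRF fields are needed (lesion identity at each biopsy, only-lesion flag). The costs are real but modest. In some patients the target sum will omit the largest lesion, and because 6.3.1 does not require non-target lesions to be measured, quantitative information on it may be lost unless its diameter is still recorded. With 24 to 29 evaluable patients per cohort, the comparison will be descriptive only.

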### **6.3.2 Methods for Evaluation of Measurable Disease**

All measurements should be taken and recorded in metric notation using a ruler or calipers. All baseline evaluations should be performed as closely as possible to the beginning of treatment and never more than 4 weeks before the beginning of the treatment.

The same method of assessment and the same technique should be used to characterize each identified and reported lesion at baseline and during follow-up. Imaging-based evaluation is preferred to evaluation by clinical examination unless the lesion(s) being followed cannot be imaged but are assessable by clinical exam.

Clinical lesions: Clinical lesions will only be considered measurable when they are superficial (e.g., skin nodules and palpable lymph nodes) and  $\geq 10$  mm diameter as assessed using calipers (e.g., skin nodules). In the case of skin lesions, documentation by color photography, including a ruler to estimate the size of the lesion, is recommended.

Chest x-ray: Lesions on chest x-ray are acceptable as measurable lesions when they are clearly defined and surrounded by aerated lung. However, CT is preferable.

Conventional CT and MRI: This guideline has defined measurability of lesions on CT scan based on the assumption that CT slice thickness is 5 mm or less. If CT scans have slice thickness greater than 5 mm, the minimum size for a measurable lesion should be twice the slice thickness. MRI is also acceptable in certain situations (e.g. for body scans).

Use of MRI remains a complex issue. MRI has excellent contrast, spatial, and temporal resolution; however, there are many image acquisition variables involved in MRI, which greatly impact image quality, lesion conspicuity, and measurement. Furthermore, the availability of MRI is variable globally. As with CT, if an MRI is performed, the technical specifications of the scanning sequences used should be optimized for the evaluation of the type and site of disease. Furthermore, as with CT, the modality used at follow-up should be the same as was used at baseline and the lesions should be measured/assessed on the same pulse sequence. It is beyond the scope of the RECIST guidelines to prescribe specific MRI pulse sequence parameters for all scanners, body parts, and diseases. Ideally, the same type of scanner should be used and the image acquisition

*Abbreviated Title: ONC201 in advanced cancers*  
*Version Date: 06/17/2020*

protocol should be followed as closely as possible to prior scans. Body scans should be performed with breath-hold scanning techniques, if possible.

PET-CT: At present, the low dose or attenuation correction CT portion of a combined PET-CT is not always of optimal diagnostic CT quality for use with RECIST measurements. However, if the site can document that the CT performed as part of a PET-CT is of identical diagnostic quality to a diagnostic CT (with IV and oral contrast), then the CT portion of the PET-CT can be used for RECIST measurements and can be used interchangeably with conventional CT in accurately measuring cancer lesions over time. Note, however, that the PET portion of the CT introduces additional data which may bias an investigator if it is not routinely or serially performed.

Ultrasound: Ultrasound is not useful in assessment of lesion size and should not be used as a method of measurement. Ultrasound examinations cannot be reproduced in their entirety for independent review at a later date and, because they are operator dependent, it cannot be guaranteed that the same technique and measurements will be taken from one assessment to the next. If new lesions are identified by ultrasound in the course of the study, confirmation by CT or MRI is advised. If there is concern about radiation exposure at CT, MRI may be used instead of CT in selected instances.

Endoscopy, Laparoscopy: The utilization of these techniques for objective tumor evaluation is not advised. However, such techniques may be useful to confirm complete pathological response when biopsies are obtained or to determine relapse in trials where recurrence following complete response (CR) or surgical resection is an endpoint.

Cytology, Histology: These techniques can be used to differentiate between partial responses (PR) and complete responses (CR) in rare cases (e.g., residual lesions in tumor types, such as germ cell tumors, where known residual benign tumors can remain).

The cytological confirmation of the neoplastic origin of any effusion that appears or worsens during treatment when the measurable tumor has met criteria for response or stable disease is mandatory to differentiate between response or stable disease (an effusion may be a side effect of the treatment) and progressive disease.

FDG-PET: While FDG-PET response assessments need additional study, it is sometimes reasonable to incorporate the use of FDG-PET scanning to complement CT scanning in assessment of progression (particularly possible 'new' disease). New lesions on the basis of FDG-PET imaging can be identified according to the following algorithm:

- a. Negative FDG-PET at baseline, with a positive FDG-PET at follow-up is a sign of PD based on a new lesion.
- b. No FDG-PET at baseline and a positive FDG-PET at follow-up: If the positive FDG-PET at follow-up corresponds to a new site of disease confirmed by CT, this is PD. If the positive FDG-PET at follow-up is not confirmed as a new site of disease on CT, additional follow-up CT scans are needed to determine if there is truly progression occurring at that site (if so, the date of PD will be the date of the initial abnormal FDG-PET scan). If the positive FDG-PET at follow-up corresponds to a pre-existing site of disease on CT that is not progressing on the basis of the anatomic images, this is not

*Abbreviated Title: ONC201 in advanced cancers*

*Version Date: 06/17/2020*

PD.

- c. FDG-PET may be used to upgrade a response to a CR in a manner similar to a biopsy in cases where a residual radiographic abnormality is thought to represent fibrosis or scarring. The use of FDG-PET in this circumstance should be prospectively described in the protocol and supported by disease-specific medical literature for the indication. However, it must be acknowledged that both approaches may lead to false positive CR due to limitations of FDG-PET and biopsy resolution/sensitivity.

Note: A 'positive' FDG-PET scan lesion means one which is FDG avid with an uptake greater than twice that of the surrounding tissue on the attenuation corrected image.

